1. STUDY OBJECTIVE AND RATIONALE

1.1 Objective

The objective of this study is to determine if residual dental plaque following brushing can be mitigated by pre-rinse with broad spectrum oral proteolytic enzyme rinse and subsequent oral pulsating waterjet appliance, enhancing the oral hygiene of patients receiving orthodontic treatment.

1.2. RATIONALE

Since the advent of modern orthodontic treatment, maintaining optimal oral hygiene has been troublesome for both the patient and the clinician. Fixed orthodontic appliances in the oral cavity are a physical barrier which can interfere with optimal oral hygiene. The tooth surface beneath the wire and adjacent to the orthodontic bracket are challenging areas for the patient to properly clean. The placement of this hardware creates obstructions and obstacles to the abrasive function of the toothbrush bristles. Poor removal of plaque adjacent to the brackets often leaves a visible halo or shadow effect on the tooth surface when the orthodontic hardware is removed. This discoloration halo (white spot lesion) is due to acidic demineralization of the tooth surface beneath the adherent dental plaque. The tooth surface beneath the bracket is protected from plaque development and resultant acidic leaching of dental minerals. Upon bracket removal, the discrepancy in tooth mineralization between these adjacent areas is now exposed creating the unaesthetic white spots. Unfortunately, many orthodontic patients to some degree, develop these unaesthetic white spots on their teeth.

The purpose of this research study is to determine if utilizing a proteolytic oral pre-rinse can hydrolyze the glycoprotein bonds which adheres the dental plaque to the dental pellicle (tooth surface in vivo). It is proposed here that the proteolytic enzyme may loosen the bond enough to allow for dislodgement by standard brushing, and further reduction in oral plaque with subsequent water jet propulsion.

The question to be answered is thus: in an adolescent patient with orthodontic appliances and poor oral hygiene, can the water jet more easily reach those areas protected from the bristles of the toothbrush (created by the orthodontic hardware) and dislodge the enzymatically loosened plaque? If so, an enzyme pre-rinse may have a place in orthodontic hygiene procedures.

The findings of this study may lead to future research studies investigating whether the addition of proteolytic enzymes can also enhance the overall oral hygiene in the general population. Possibly removing plaque between teeth and other areas where brushing alone can't reach.

It is well known that upon initiation of fixed orthodontic appliance therapy there is a significant increase in dental plaque accumulation, in which patient education and oral hygiene instruction alone has proven insufficient to overcome(1). Poor oral hygiene during orthodontic treatment results in a high prevalence of white spot lesions on anterior tooth surfaces surrounding brackets. Martignon et al showed 96% of patients had one or more white spot lesions following orthodontic treatment (2).

The problem appears to be that the orthodontic wire and bracket impede the toothbrush bristles from close contact with an otherwise naturally smooth tooth surface. This hardware interferes with the mechanical contact and abrasive function of the toothbrush bristles to dislodge adherent dental plaque from the tooth surface. Residual plaque following brushing in orthodontic patients has been found along the gum line, around brackets and beneath wires(3).

The orthodontic wires make flossing an arduous task, which is why many patients give up and never adequately remove dental plaque from orthodontic hardware and dental contact points. Numerous studies have correlated fixed orthodontic treatment with less than optimal oral hygiene (4). Orthodontic induced gingivitis(5) (7) typically develops within the first few months of fixed appliance placement(6). Following the placement of the orthodontic fixed appliance, the resultant change in oral hygiene creates an environment favorable to *Streptococcus mutans*(8) and an increase in gram negative bacteria which are associated with periodontal disease(9). Improved oral hygiene would likely prevent many adverse sequelae commonly associated with orthodontic treatment (2).

Previous studies have used pre-rinsing agents as an oral hygiene adjunct and demonstrated mixed results. Boyd found Hydrogen peroxide-sodium fluoride rinse is more effective than sodium fluoride rinse alone in preventing gingivitis and decalcification in adolescent orthodontic patients(10). Miranda, conducted a trial using water, Listerine, or Plax, as pre-rinse agents and concluded that pre-rinsing in children demonstrated no difference in plaque removal (11). However, Tufekci showed the addition of Listerine rinse to an oral hygiene protocol significantly reduced plaque (more than just brushing and flossing alone in orthodontic patients). He concluded that the addition of Listerine was helpful for fixed orthodontic patients to reduce their risk of white spots development and gingivitis (12). Pontier's study concluded there was no difference between pre-rinse (Plax TM versus placebo) for plaque removal in orthodontic patients(13).

Water irrigation (pulsating water jet therapy), another adjunct to oral hygiene, has demonstrated a significant difference in biofilm (14) and plaque removal - especially in difficult to reach dental plaque retention areas, such as around the orthodontic brackets and wires (6). The plaque removal was also increased utilizing a specialized orthodontic water jet tip as compared to a standard water jet tip (15).

Surprisingly little has been investigated concerning proteolytic hydrolysis (to loosen the dental biofilm) influence on oral hygiene (16). No published studies could be located (PubMed) that involve use of proteases as a plaque removal aid in the orthodontic patient. Literature search revealed a study of Krillase (enzyme obtained from ocean krill) included in a chewing gum to reduce gingivitis and plaque acumination (17). Published articles utilizing the plant enzyme papain in orthodontics include: orthodontic bonding and sheer bond strength study (18) and the effect of different concentrations of papain gel have on orthodontic bracket adhesion study (19).

Papain and Bromelain are naturally occurring serine proteases. Papain is derived from the latex from green papaya fruit (*Carica papaya*) while bromelain is obtained from pineapple stalks (*Ananas comosus*). Because of their innate proteolytic activity, papain and bromelain have been used extensively in the food and medical industries. Both enzymes are included on the FDA's "Generally Recognized as Safe" (GRAS) list. Both bromelain and papain are used commercially for tenderizing meat and producing protein hydrolysates (20). These proteolytic enzymes have a broad range of substrate specificity, which easily and efficiently hydrolyze

most soluble proteins, yielding peptides and amino acids byproducts.

Other uses of these enzymes are in toothpaste (papain/bromelain combination as the active ingredient) for extrinsic enamel stain removal (21, 22)(23). These enzymes have also been used for wound debridement for of damaged collagen and necrotic tissue in humans (24). Finally, health food enthusiasts claim dietary supplementation with papain and bromelain may be useful in alleviating joint pain and inflammation and supplementing natural digestive proteases.

1.3. Potential Risks and Benefits

1.3.1. Potential Risks

Product Risks

Irritation of the oral cavity can occur, (also known as stomatitis or angular chelitis), and has occurred among those individuals who eat extraordinary amounts of fresh pineapple. The use of an active protease in an oral rinse may cause stomatitis or angular chelitis and possibly irritate an undetected oral ulcer and cause the subject discomfort.

Adverse reactions

Hypersensitivity/allergic reactions have been reported in individuals who have supplemented their diet with bromelain and are allergic to pineapple. Nausea, vomiting, and diarrhea were reported in such instances following ingestion.

Contraindications

Use of bromelain is contraindicated in those who are hypersensitive or allergic to pineapple or proteases. Gastrointestinal or oral ulcers, use of anticoagulant/blood thinner medication, antibiotics or anticipating surgery would also be contraindications to ingestion of active proteases.

Precautions

Bromelain has a long history of being used in the food industry and no serious side effects or deaths have been reported. Nevertheless, certain precautions will be taken in using this natural protease.

Rinses will be expectorated. Only a negligible amount of enzyme may be ingested unless the test subject inadvertently swallows the solution. Even in this scenario, this should not be a problem since quantities in greater amounts are frequently ingested by individuals wishing to supplement their natural pancreatic digestive capabilities.

Interactions

Since bromelain is an active serine protease, it is susceptible to inactivation or denaturation by excessive heat, chemicals or ions. Therefore, the oral rinse test solutions will not have alcohol or fluorine compounded within the solution tested.

Over dosage

Bromelain has been shown to be safe when ingested in less than 130,000 FCC papain units per day (approximately 1.5 g of enzyme preparation). Symptoms of over dosage using bromelain as an oral rinse would include development of oral ulcers, stomatitis or angular chelitis. This would produce mild discomfort for a few days while the oral mucosa regenerates.

Additional Risks

Additional potential risk to the subjects include cross contamination. This risk will be managed by the use of experienced IU dental personnel proctoring the test subjects, whom will follow strict infection control guidelines outlined by the IU School of Dentistry. This includes handwashing between subjects, use of single use nitrile gloves, and facemasks (for researchers) during the intraoral exam. Vials and cheek retractors will be single use.

Loss of confidentiality of private information collected is another risk. To counter this risk, all data collected on paper will be stored in a locked area and limited to study personnel. Electronic data will be stored in an encrypted, password protected computer file with access limited to study personnel. All records will be identified by study number only. A master list will be maintained which will match the subject to their study number and this list will be stored in a secured area.

1.4. Adequacy of Protection against Risks

To limit the potential risks of ingestion of the active ingredients, persons with the following conditions will be excluded from participation in the study:

- 1. gastrointestinal or oral ulcer
- 2. taking an anticoagulant/blood thinner medication or antibiotics
- 3. anticipating surgery in the next six months
- 4. allergic to proteolytic enzymes, pineapples or disclosing agent
- 5. pregnant, breastfeeding or intending to become pregnant in the next six months

1.5. Known Potential Benefits

There is no known benefit for the subject.

2. STUDY DESIGN

This will be a single site, cross-over, double-blind study with up to 55 subjects enrolled in the study. Since each person varies with technique and diligence in brushing their teeth, each subject will serve as their own control in this cross-over study. There will be at least a week time interval between the two arms of the study (length of wash out phase: one week). The study will be completed over the course of two weeks. Each step in the protocol will be timed to reduce inter- and intra-subject variability. Toothbrushes used in the study will be uniform, a new tooth brush will be used at each arm of the study. All oral hygiene aids will be of the same brand to eliminate variability (eg: all toothbrushes will be of the same brand, all disclosing tablets of the same brand, etc). For standardization and optimal photography, the same type of cheek retractor and digital camera will be used for all subjects.

Hypothesis

Null: There is no statistically significant difference in visual plaque scores with or without use of a proteolytic enzyme rinse aid.

Alternative: There is a statistically significant difference in visual plaque scores with use of proteolytic enzyme rinse aid.

Product Description

This study will use bromelain as the proteolytic enzyme in the oral rinse. Bromelain is an enzyme naturally found in high concentration in the stem of pineapples. This proteolytic, proteindigesting enzyme breaks down (hydrolyzes) proteins by reducing large complex proteins into smaller peptides or individual amino acids (25). For this reason, bromelain is commonly used as a digestive aid, (in pill form) or (in powder form) as a meat tenderizer.

- 1. The subject will then be asked to use a water jet cleansing device (WaterPik). This will also

be timed (two minutes). The instructions given to the subject: "Use this Waterpik to clean around the brackets and under the wires as best you can". All Waterpik devices will be set at the same medium pulsating pressure.

- m. Fourth frontal photograph for this visit obtained (including another random serial identifying number unique for subject, stage and visit).
- n. Subject receives \$25 Visa gift card and dismissed.
- o. Subject (or guardian) is phoned later that day & questioned if they have any concerns or side effects. Subject & Guardian are reminded of phone number contact of student researcher.

Second Visit (1week later)

a. Each subject will repeat the procedure as described above on the subsequent visit (a-n) with the second (vial) oral rinse treatment (placebo or enzyme).

3. STUDY POPULATION

3.1. Source and Number of Subjects

55 adolescent and young adult subjects (10-25 years, male or female). Subjects will be in active fixed (edgewise) orthodontic appliances at the Indiana University School Dentistry.

3.2. Subject-Selection Criteria

Inclusion Criteria

Individuals may qualify to participate in the study if they meet all the following requirements:

- Subject is willing to consent
- male or female
- age range from 10-25 years
- willing to follow study instructions
- in active orthodontic treatment with fixed orthodontic appliances
- patient at Indiana University School of Dentistry Orthodontic Clinic

Exclusion Criteria

Individuals will be excluded from participation if they possess any of the following conditions:

- pregnancy, breast feeding or intending to become pregnant in the next six month period
- latex allergy
- not willing/able to follow study instructions
- pineapple allergy
- proteolytic enzymes allergy
- food dye allergies (to assure no issues with using disclosing solution)
- smoker
- has a gastrointestinal or oral ulcer
- is taking an anticoagulant/blood thinner medication or antibiotics
- is anticipating surgery in the next six months
- person with dental training (dental students, hygiene students, faculty, & assistants)

3.3 Subject Recruitment

Potential subjects will be recruited from patients at the Indiana University School of Dentistry Orthodontic Department. Recruitment methods will include the following:

- 1) An IRB approved flyer will be hung in the waiting room and various locations within the clinic.
- 2) The student investigator will call patients who are her patients in the clinic to determine interest.
- 3) All residents and faculty will assist in distributing an IRB approved flyer that contains a section with contact information for the subject to complete if they are interested in learning more about the study. Potential subjects will be able to place completed interest forms with their contact phone number in a secured drop box in the clinic for the student investigator to access. The student investigator will then call the potential subjects to discuss the study.

In all cases, the student investigator will use an IRB approved telephone script to review the study with the potential subjects. If the potential subject is interested in participating, and if time allows, the consent and assent will be sent to the potential subject by mail so they will have the opportunity to review the information before their appointment. Consenting and assenting, as applicable, will occur in the clinic prior to any study procedures being performed. Consenting may also occur by phone, using the consent documents sent by mail. Test subjects will attend two testing visits approximately one week apart. These visits will be outside from their normal orthodontic visits.

Subjects will be compensated for their time in the study by gift of the testing Waterpik appliance they used and \$50 (\$25 per visit) for participating in the study. Payment will be in the form of Visa gift cards.

4. TEST TREATMENTS

4.1. Administration of Study Investigational Product

The components of each treatment will be formulated prior to treatment and placed in a plastic vial. Each of the vials for the oral rinse treatments will be labeled with a unique set of numbers for subject and stage of treatment (only decoded by use of master list).

4.2. Blinding/Unblinding Procedures

To eliminate potential human bias, photos will be graded independently by one examiner from Indiana University School of Dentistry with dental clinical experience. The examiner will be blinded with regard to the stage and visit of the oral hygiene procedures. The identification on the photos will not allow the examiner to know which photos came from the same subject, which series they are evaluating (baseline staining, post-rinse, post-brush, post-Waterpik) and which treatment.

Each photo will be independently reviewed and scored assessing the degree of plaque staining from one to five. An example photograph of each degree (1-5) will be given to the examiner for standardization.

The researchers and subjects will be blinded to knowing which vial has the proteolytic enzyme treatment. The subsequent visit the subject will receive the second vial. The study records will be maintained by this committee member ([name]).

Each photograph will be labeled by only a serial number and can only identified through use of a master sheet. Each subject will have eight randomly assigned serial numbers corresponding to each testing step and visit (two different study visits with four photographs each).

4.3 Photo Labeling

A photographic sequence identifier (A-D) will be added to the patient's random subject ID to properly log and sequence the obtained photographs. The following codes will be utilized in the study:

- A: After use of the disclosing tablet
- B: After 2 minute rinse with provided solution
- C: After brushing
- D: After the use of the WaterPik

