4.5. Randomization Procedures

Subjects will be stratified randomly by sex and age groups. Subjects will be allocated random sets of serial numbers kept on a master list which will be retained in a secured location. The faculty member grading the photographs will be given the 440 photographs completely in random order, randomized by the primary investigator.

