5. STUDY METHODOLOGY

5.1. Preparation of Investigational Products

The dry components of each rinse will be formulated prior to study and placed in a plastic vial with lid. The statistician will generate a second randomization list to identify which vial (A or B) the patient will receive at the first and second visits, respectively.

Prior to beginning the study, the dry powdered components for each treatment rinse will be weighed and placed into clean 20 mL vials, (for both the enzymatic and placebo rinse) and sealed with plastic caps. This will prevent contamination or spillage. All vials will be prepared at one time in a clean room prior to the study.

Selected committee members will measure out one gram of enzyme and one gram of placebo (powdered sugar) for each subject. Both the placebo and the proteolytic rinse compounds will be weighed, formulated and placed into darkened 20 mL vials with a plastic top. Each vial will then be assigned the appropriate code (Product A or Product B) by the co-investigator [name] Only this investigator ([name]) will know the identity of the vial contents and will share this information with the statistician at the time of statistical analysis. The formulated compounds placed in the clean vials will be stored in a locked secured location.

Manufacture of Bromelain Rinse:

The bromelain enzyme will be obtained (donated) in bulk powder form from Ultra Bio-logics Inc. (Chateauguay, Quebec, Canada). The Ultra Bio-logic bulk bromelain concentrated supplement is standardized (by manufacturer) to 2400 Gelatin Digesting Units (GDU)/gram. The strength of an enzyme is quantified in GDU/gram units. GDU/gram tells us how much protein a gram of bromelain can digest. The proteolytic rinse will contain one gram of bromelain brought into solution with 15ml of pineapple juice. One gram of bromelain is within the recommended daily dosage for oral consumption by the manufacturer-

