5.4. Oral Photography Process

Standardization of photographs: all photographs will be taken from the same angle (frontal), to include only the teeth and lips of the subject, with a single use, hands-free cheek retractor. Subject will be partially open so that the lower dentition is fully visible for photography. Each photograph will be at the same magnification (see 10.4). The adhesive label with the corresponding serial number will be placed on the subject's chin and will be included in the photograph.

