6.2. Dental Plaque Evaluation and Data Management

Teeth will be disclosed and the facial tooth surfaces will be graded for visual plaque. Incisors (#s: 7-10 and 23-26) will be visually evaluated on digital photographs and assigned a score (0-4) according to the orthodontic plaque index (see figure 1 below). Examiner will be given a visual scale of comparison, which corresponds with the Orthodontic Plaque Index (OPI) for diagnosing dental plaque around orthodontic brackets. Each tooth will each receive an individual score, in addition all tooth scores will be added together to calculate a composite score for upper incisor and lower incisor segments. All recorded plaque scores will be recorded in an excel document on a password protected laptop computer by the grader.

To eliminate potential human bias, a single examiner from the Indiana University School of Dentistry with clinical dental experience, will judge each photograph. This examiner will be

blinded with regard to the stage of the oral hygiene procedure as described above.

Data/digital photographs will be viewed on the same computer and will be backed up daily onto a secure box.iu.edu health account, which will only be accessible to researchers and by two step authentications and passphrase. Research laptop will remain in secure location and locked whenever not in use.

Plaque scoring:

Figure 1: Orthodontic Plaque index scoring system(Beberhold).

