- 2) Post-treatment rinse (enzyme or placebo) photograph.
- 3) Post- brushing photograph.
- 4) Post-Waterpik photograph.

Each photograph will be independently reviewed using the same computer and scored assessing the degree of plaque according to the Orthodontic Plaque index method by a single examiner.

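### Does the stage letter in section 4.3's photo code unblind the examiner, against section 4.2?

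*Combined protocol and SAP*

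**What the plan says.** Section 4.2 sets the rule for what the examiner may see: "Each photograph will be labeled by only a serial number and can only identified through use of a master sheet". It adds the purpose: "The identification on the photos will not allow the examiner to know which photos came from the same subject, which series they are evaluating", and it extends this to treatment. Each subject has eight serial numbers, one for each of four stages at each of two visits; section 9.4 repeats the eight.

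The protocol also says what appears in the image. Section 5.4 states: "The adhesive label with the corresponding serial number will be placed on the subject's chin and will be included in the photograph". The visit schedule in section 2.1 asks for a new random number at each photograph, unique to subject, stage and visit. Section 5.2 has these numbers prepared in advance, four attached to each of the subject's two vials.

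On grading, section 4.5 states: "The faculty member grading the photographs will be given the 440 photographs completely in random order, randomized by the primary investigator". The examiner works on one computer (section 9.4), and under section 6.2 "All recorded plaque scores will be recorded in an excel document on a password protected laptop computer by the grader".

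Section 4.3 then describes a second code: "A photographic sequence identifier (A-D) will be added to the patient's random subject ID to properly log and sequence the obtained photographs". It lists A to D as the four stages in order. It does not say where the code is written, nor that the examiner never sees it.

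**The concern.** The efficacy outcome is one examiner's visual score. If the code in section 4.3 were on the chin label, in the image file name or in the scoring sheet, the examiner could read the stage of every photograph and group photographs by subject. Section 4.2 forbids both. Random presentation order would not help, because the letter travels with the image. An examiner who expects plaque to fall from A to D might score to that expectation, and stage and treatment-by-stage are terms in the ANOVA of section 8.2.

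The heading of section 4.3 invites this reading, and no section names the identifier used for file names or score rows. There are two lesser worries. The code has no visit element, and its letters A and B are also the product codes of section 5.1.

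**Working it through.** **1. The plan's own count.** Inputs: 55 subjects (sections 3.1 and 8.1), 2 visits and 4 photographs per visit (section 9.4).

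- Photographs: 55 x 2 x 4 = 440, which agrees with section 4.5.
- Serial numbers per subject: 2 x 4 = 8, which agrees with sections 4.2 and 9.4.
- With the 45 completers of section 8.1: 45 x 8 = 360 photographs.

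**2. Can the section 4.3 code be the identifier on the photograph?** Assume one subject ID for both visits; the protocol does not state this.

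- Codes from ID plus letter: 55 x 4 = 220.
- Photographs per code: 440 / 220 = 2.

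Section 2.1 requires the number in the image to be unique for subject, stage and visit. On this assumption a code shared by two photographs cannot meet that requirement, so the code is something additional to the serial number.

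**3. Where does each section place its identifier?**

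| Section | Identifier | Stated place or use |
|---|---|---|
| 2.1 | random number, new at each photograph | in the photograph |
| 4.2 | serial number alone | label of the photograph, decoded by master sheet |
| 5.2 | four of the subject's random numbers per vial | attached to the vial |
| 5.4 | serial number | chin label, in frame |
| 9.4 | eight serial numbers per subject | to tell the photographs apart |
| 4.3 | subject ID plus A-D | to log and sequence |

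Only section 4.3 gives a record-keeping purpose, and it never says that its code goes on the image. If it is a log entry, all six rows can be followed together. If it is written on the photograph, section 4.2 is broken. The first reading satisfies the whole protocol.

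**4. What if the letter leaked anyway?** Suppose knowledge of stage shifts the examiner's score by an amount b_s that depends on stage s. The enzyme-minus-placebo difference at that stage is

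(mu_E,s + b_s) - (mu_P,s + b_s) = mu_E,s - mu_P,s.

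The shift cancels. The comparison powered in section 8.1 is after the water jet, where every photograph in both arms would carry the letter D. The stage main effect would be exposed, but the hypothesis in section 2 concerns plaque scores with and without the enzyme. The cancellation assumes a shift that adds equally in both arms. A shift that depended on the plaque level itself could change the size of the difference, but the letter gives the examiner no means of favouring one rinse.

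**5. The lesser points.** The eight serial numbers already separate the visits, so the missing visit element in a log code loses nothing. Letters A and B cover 55 x 2 visits x 2 letters = 220 of the 440 photographs, but product codes belong to vials and stage letters to photographs. No section puts both in one field.

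**The case for a change.** The best case for a change is that section 4.3 nowhere states the log-only reading. Its heading points to the photograph, and staff could name image files by ID and letter in good faith. The examiner opens files and fills a spreadsheet, and the protocol is silent on the identifier in either place. The efficacy data rest on one person's judgement, so the blinding text ought to be airtight, and two sentences would make it so.

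Part of this stands. Section 4.3 is unclear, its heading is unfortunate, and file naming is not described. A letter that reached the examiner would reveal stage.

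The rest does not carry. Staff do not read section 4.3 alone. The section just before it forbids any identification on the photographs that shows subject or stage, and a file named by ID and letter would breach that. For the score row, the only identifier the protocol puts before the examiner is the serial number in the image. Nor would perfect labelling hide all linkage between one subject's photographs, because section 9.4 has the same teeth, with appliances in place, shown every time.

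**Conclusion.** This is an ambiguity in one sentence, not a contradiction, and it calls for no change. Followed as a whole, the protocol keeps the stage code in the log and gives the examiner serial numbers only. On that reading 0 of 440 photographs show their stage, and the sample size, power and analysis are untouched. If someone put the code on labels or files against section 4.2, stage would be readable on all 440 photographs (360 with 45 completers). The documents give no basis for the size of any resulting bias, and the letter would still not reveal the rinse.

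The conclusion rests on two assumptions: that staff apply section 4.2 as the governing rule for anything the examiner handles, and, for the leak scenario, that an expectation about stage acts alike in both arms. A clarifying sentence would do no harm, but it would only restate what section 4.2 already requires. The visit element and the shared letters have no shown consequence.
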